7.1.2. Influenza Symptoms

The maximum severity of influenza symptoms during the challenge period, reported as part of the Modified Jackson Score and used to determine the AR, will be summarized by challenge dose group in [Table 15](#), and separately by infection status (see [Section 3.2.3](#)) in [Table 16](#) and [Figure 7](#) (infected participants) and [Table 17](#) and [Figure 8](#) (uninfected participants). Symptoms reported on Study Day 15 will be presented similarly in [Table 18](#) and [Table 19](#). Symptoms over the challenge period will also be summarized by infection status, independent of challenge dose group, in [Table 20](#), and Day 15 symptoms will be presented in [Table 21](#).

New-onset symptoms (see [Section 3.2.3](#)) among infected participants will be summarized in [Figure 9](#), and the maximum severity of symptoms will be summarized by concurrent infection status in [Table 26](#). Wilcoxon signed rank tests will be used to compare maximum severities among infected participants: pre-infection to during infection, post-infection to during infection, and pre-infection to post-infection, in [Table 27](#). No p-value adjustment is planned for multiple comparisons, but the number of comparisons made will be considered when interpreting the results. Current/concurrent infection status is defined in [Section 3.2.3](#).

The maximum symptom severities reported for each study day during the challenge period and at any point post-challenge will be summarized for currently infected participants, separately by challenge dose group in [Table 22](#) through [Table 25](#). At baseline and Day 1, all participants will be included in these summaries, as a comparison for post-infection symptoms.

Total MJS scores during the challenge period will be presented by study day and challenge group in [Figure 10](#), with RT-PCR+ study days indicated with annotation in the given cell.

MJS symptoms will be presented in detail in [Listing 8](#).

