# 9.5.4.4 Exploratory Physiological and Additional Clinical Endpoints

Additional exploratory analysis of clinical endpoints will include cross-tabulations of symptoms as collected by each of the two scoring systems, separately by viral shedding status (as determined by RT-PCR), by receipt of active challenge virus or placebo, and across all subjects. To examine the ability of each scoring algorithm to accurately capture symptomatic influenza/MMID, the symptom scores (i.e., severity) for each symptom will be summarized by RT-PCR status. These summaries will be made on a by-visit level and for the maximum severity/score of each symptom over the entire challenge period.

Alternative case definitions for symptomatic influenza virus infection will be explored via development of clinical scoring algorithms based on each of the scoring scales. A training and testing approach will be utilized to determine multi-symptom models predictive of RT-PCR positivity, using the maximum severity observed over the challenge period for each symptom. This approach will be applied separately for each scoring scale, and the operating characteristics of the final multi-symptom models will be compared.

Physiological data, as collected by the wearable devices, will be summarized by dose group and by symptomatic influenza status, separately. Further exploratory analysis of these data will be described in the SAP.

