3.2.3. Infection Status

Infection status, independent of symptom status, will be defined at the participant level in two different ways:

- Participants are considered **Infected** if viral shedding is detected in NP swab(s) by qualitative and/or quantitative RT-PCR on at least two days beginning 24 hours after challenge until Study Day 8
- Participants are considered to be **Currently Infected** from their first through their last study days meeting the viral shedding definition above (and in [Section 3.2.2](#)), regardless of any intermittent negative results between those two study days.

Pre-infection and post-infection results will be determined based on the definition of Current Infection above. New-onset symptoms will be those with a maximum severity post-infection (starting on the day of first RT-PCR positivity) above that of baseline, for infected participants.

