5. GENERAL STATISTICAL CONSIDERATIONS

5.1. General Principles

The challenge period is defined as the day of study challenge (Day 1) through discharge from the confinement period (Day 8 or later).

Continuous variables will generally be summarized using the following descriptive statistics: non-missing sample size (denoted by “n”), mean or geometric mean, standard deviation, minimum, median, and maximum. Titers will be summarized with geometric means, first across replicates to compute one value for each individual sample and then across participants within clinical outcome groups. The frequencies and percentages (based on the non-missing sample size) of observed levels will be reported for categorical measures. Data listings will typically be sorted by site or other grouping variable (e.g. infection status), participant, and by visit number within participant, where appropriate. All tables will be annotated with the total population size relevant to that table, including any missing observations.

For continuous variables, confidence intervals will be computed based on the t-distribution, unless the data appear especially non-normal and the sample sizes for the analysis are insufficient to apply the central limit theorem. Bootstrap confidence intervals may be calculated instead if the t-distribution is determined to be unsuitable. For binary variables, confidence intervals will be computed using the exact Clopper-Pearson method.

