7.2.3. Alternative Definitions of Symptomatic Influenza Infection

While the study was not powered to establish a predictive signature of symptoms for influenza infection, exploratory analysis will be conducted to determine a predictive multi-symptom model to validate in an independent influenza challenge study.

To predict infection status, as defined by two or more days with RT-PCR+ results, the maximum severity of each symptom reported during current infection (for infected participants) or across the entire challenge period (for uninfected participants) will be included as candidate predictors in a penalized logistic regression model (lasso) [4]. The penalization parameter will be selected based on 10-fold cross-validation. The resultant model will be refit without penalization to remove the bias in estimation of the coefficients caused by the penalization parameter, with estimated odds ratios presented in [Table 46](#). The internal performance of the model in the training set will be shown in the receiver operating characteristic (ROC) curve in [Figure 15](#). The optimal cutpoint from the model, as determined by Youden's J statistic [5], will be used in a future validation of these results.

Additionally, the MMID-2 outcome will be compared with the primary symptomatic influenza infection outcome in [Table 47](#). Sensitivity analyses will also be conducted to assess varying thresholds for MJS scores and, separately, for the number of days of detectable viral shedding ([Table 14](#)).

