[Repeat for any additional symptom(s) selected in lasso procedure]

Notes: XX participants in the Safety population included in the model; the infection outcome is defined as two or more study days with RT-PCR+ tests at any point during the challenge period. The maximum severity of each MJS symptom during the infection period, or across the challenge period for the uninfected participants, is utilized in the set of candidate predictors.

The optimal value for the penalization parameter determined using 10-fold cross-validation.

Unbiased coefficient estimates obtained by refitting selected covariates in logistic regression model.

Hosmer and Lemeshow Goodness of Fit p-value = 0.xxx.

Table 47: Comparison of Symptomatic Influenza Infection to Mild-to-Moderate Influenza Disease, Safety Population

Variable	10 ⁴ TCID ₅₀ Challenge Virus (N=X)		10 ⁵ TCID ₅₀ Challenge Virus (N=X)		10 ⁶ TCID ₅₀ Challenge Virus (N=X)		Sham Inoculum (N=X)		All Participants (N=X)	
	MMID-2 n (%)	No MMID-2 n (%)	MMID-2 n (%)	No MMID-2 n (%)	MMID-2 n (%)	No MMID-2 n (%)	MMID-2 n (%)	No MMID-2 n (%)	MMID-2 n (%)	No MMID-2 n (%)
Symptomatic Influenza Infection	x (x.x)	x (x.x)	x (x.x)	x (x.x)	x (x.x)	x (x.x)	x (x.x)	x (x.x)	x (x.x)	x (x.x)
No Symptomatic Influenza Infection	x (x.x)	x (x.x)	x (x.x)	x (x.x)	x (x.x)	x (x.x)	x (x.x)	x (x.x)	x (x.x)	x (x.x)

Notes: N = Number of participants in the Safety population; n = Number of participants reporting the given combination of Symptomatic Influenza Infection and MMID-2 outcomes after challenge.

Table 48: Logistic Regression Model to Assess the Associations Between Baseline Characteristics and Development of Symptomatic Influenza Infection, Safety Population

Model Parameter	Parameter Estimate	SE	p-value	Odds Ratio	95% CI
Intercept	x.xx	x.xx	x.***	-	-
Challenge Virus Dose (TCID ₅₀)	x.xx	x.xx	x.***	x.xx	(x.xx, x.xx)
Age at Baseline (Years)	x.xx	x.xx	x.***	x.xx	(x.xx, x.xx)
Sex (Male vs. Female)	x.xx	x.xx	x.***	x.xx	(x.xx, x.xx)
Prior Receipt of Seasonal Influenza Vaccine or Viral Challenge (Yes vs. No)	x.xx	x.xx	x.***	x.xx	(x.xx, x.xx)
Clinical Site (UMD vs. DU)	x.xx	x.xx	x.***	x.xx	(x.xx, x.xx)

Notes: XX participants in the Safety population included in the model; the symptomatic influenza infection outcome is defined as two or more study days with RT-PCR+ tests and, separately, a cumulative Modified Jackson Score of at least 6 over any 5-day window during the challenge period. Hosmer and Lemeshow Goodness of Fit p-value = 0.xxx.

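### Table 27 and the symptom lasso use symptom maxima over windows of unequal length, and Table 46 ignores the selection step

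*SAP*

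**What the plan says.** SAP 3.2.3 treats an infected participant as currently infected "from their first through their last study days meeting the viral shedding definition above" and adds: "Pre-infection and post-infection results will be determined based on the definition of Current Infection above". No phase has a fixed length. SAP 7.1.2 then states: "Wilcoxon signed rank tests will be used to compare maximum severities among infected participants: pre-infection to during infection, post-infection to during infection". Pre- against post-infection is the third contrast, and no p-value adjustment is planned. The Table 27 shell has 15 rows, so 15 × 3 = 45 p-values. SAP 5.1 sets the outer limits: "The challenge period is defined as the day of study challenge (Day 1) through discharge from the confinement period (Day 8 or later").

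For the exploratory symptom model, SAP 7.2.3 takes as candidate predictors "the maximum severity of each symptom reported during current infection (for infected participants) or across the entire challenge period (for uninfected participants"), in a lasso tuned by 10-fold cross-validation. It continues: "The resultant model will be refit without penalization to remove the bias in estimation of the coefficients caused by the penalization parameter". Table 46 prints a standard error, p-value, odds ratio and 95% CI for each selected symptom, with the note: "Unbiased coefficient estimates obtained by refitting selected covariates in logistic regression model". The ROC curve is labelled as training-set performance, and the Youden cut-point goes to a later validation.

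Protocol 9.5.4.4 planned this differently: "A training and testing approach will be utilized to determine multi-symptom models predictive of RT-PCR positivity". There, each symptom's maximum was taken over the challenge period, whatever the infection status. SAP section 14 nevertheless reports no substantive change from the protocol's analyses.

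**The concern.** The maximum of a daily score can only rise as days are added. If the infection phase is several days long and the phases around it are short, the maximum during infection tends to be larger even when infection does nothing. The signed-rank tests then measure days observed as well as illness. Their p-values bear on whether symptoms come from infection, and they sit under the primary clinical analysis.

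In the lasso the window depends on the outcome. An infected person contributes only shedding days; an uninfected person contributes the whole challenge period. Such a predictor cannot be computed for a new person whose infection status is unknown, which is the situation the model is meant for. Uninfected windows are generally the longer ones, so the artefact pushes symptoms towards predicting no infection.

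Refitting without the penalty removes shrinkage. It does not remove the bias from choosing symptoms because they looked associated in the same data, so ordinary p-values and intervals are too optimistic. The cut-point sent for validation comes from that same fit.

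**Working it through.** The plan gives no figure for this point, so there is none to reproduce. All settings below have **no infection effect**.

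**Assumptions not in the documents.** Daily symptom probability 0.1 to 0.3; severity 1/2/3 in 75/20/5% of symptomatic days; within-person correlation (ICC) 0 to 0.6; 20, 40 or 60 infected; first positive on Day 2/3/4 in 50/35/15%; last positive on Days 5 to 8; discharge on the later of Day 8 or the day after the last positive. These give:
- pre-infection, counted from Day 1: 1 to 3 days, mean 0.50×1 + 0.35×2 + 0.15×3 = 1.65;
- during infection: 2 to 7 days;
- post-infection: 1 to 3 days.

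**Step 1, exact, independent days.** If F(s) is the chance that one day's score is at most s, the maximum over k days has distribution F(s)^k. With daily probability 0.2, F(0), F(1), F(2) = 0.80, 0.95, 0.99. Over five days these become 0.328, 0.774, 0.951. For one pre-infection day against five infection days:
- P(during > pre) = 0.80×(1−0.328) + 0.15×(1−0.774) + 0.04×(1−0.951) = 0.574
- P(during < pre) = 0.15×0.328 + 0.04×0.774 + 0.01×0.951 = 0.090

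With equal windows these two would be equal.

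**Step 2, Table 27 simulated.** 2,000 trials per setting, two-sided 5%. The level comes from Protocol 9.5.1, because the SAP states none for Table 27. The last column counts pre-infection from Day 1.

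| Setting | During vs pre (from Day 1) | During vs pre (from Day -2) | During vs post | Pre vs post |
|---|---|---|---|---|
| 20 infected, p=0.1, ICC 0.3 | 18.2% | 4.8% | 16.0% | 2.1% |
| 40 infected, p=0.2, ICC 0.3 | 65.6% | 10.3% | 62.7% | 5.1% |
| All settings | 6.5–97.6% | 1.5–18.2% | 6.0–97.1% | 0.8–5.7% |

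**Step 3, alternatives for Table 27.** One pre-specified day against one day gives 0.5% to 6.1%. Mean daily severity in place of the maximum, during against pre, gives 1.9% to 11.6%. Some inflation remains because the signed-rank test needs symmetric differences.

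**Step 4, lasso simulated.** 200 trials per setting; 62 participants (50% infected) or 90 (60% infected); 12 symptoms; daily probability 0.1 to 0.2; ICC 0.3 to 0.6. The penalty minimises cross-validated error; the SAP does not name a rule.

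| Result | SAP windows | Days 2–8 for all |
|---|---|---|
| Any symptom selected | 56–81% | 36–44% |
| Selected coefficients that are negative | 86–95% | 46–57% |
| At least one refit p<0.05 | 50–78% | 29–37% |
| Mean training AUC | 0.64–0.73 | 0.57–0.58 |

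The common window removes the lean towards negative coefficients. It does not cure selection: about a third of null trials still show a refit p<0.05, and when something is selected the training AUC averages 0.68 to 0.71 although the symptoms carry no information.

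**The case against.** The best defence is that little rests on these analyses. SAP 5.8 calls the analysis primarily descriptive, and Protocol 9.5.1 calls hypothesis tests exploratory. SAP 7.2.3 says the study was not powered to establish a signature, labels the ROC as training-set and plans validation in an independent study. Other displays are much less exposed to window length: symptoms by study day (Tables 22 to 25), mean scores by day (Figure 13), and the area under the Modified Jackson Score curve, which SAP 3.2.5 scales by days. The text of 7.2.3 claims only to remove bias due to the penalty; only the Table 46 note goes further. All of this stands and limits the stakes. It does not make the Table 27 p-values or the lasso predictor correct, and the scaling in SAP 3.2.5 is not applied to the maxima.

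Second, the pre-infection phase may include baseline. Modified Jackson scores are collected from Day -2, and SAP 3.2.3 compares new-onset symptoms with baseline. Table 26's title is limited to the challenge period; Table 27's is not, although its first footnote mentions that period. On that reading during vs pre is far less inflated. The SAP does not settle the matter, and during vs post is unchanged.

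Third, the sizes depend on assumed rates, and the low end is close to 5%. That stands for size, but not for direction.

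A reader might also infer more than the documents support:
- That every Table 27 test is inflated. Pre vs post is near nominal when pre-infection starts on Day 1.
- That Table 27 windows depend on infection status. The table covers infected participants only, so they depend on phase; only the lasso window depends on status.
- That the lasso would manufacture a positive symptom signature. The artefact runs mostly the other way.
- That the ROC is concealed or void. It is openly labelled; the fault is optimism.

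**Conclusion.** The plan is wrong as written in three respects.

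1. Two of the three Table 27 contrasts compare maxima over unequal windows and, in most settings examined, reject well above 5% with no infection effect. If Days -2 and -1 count as pre-infection, during vs pre falls to about 2% to 18%, while during vs post stays inflated. Pre vs post was not calculated on that reading.
2. The lasso predictor is defined by the outcome and biased against infection, so true symptoms would be attenuated or reversed. It departs from the common window and testing step of Protocol 9.5.4.4.
3. Table 46 inference ignores selection, its note on unbiasedness is wrong, and the training ROC and its cut-point are optimistic.

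The mechanism follows from the SAP's definitions. The percentages rest on assumed symptom rates, within-person correlation, numbers infected and shedding duration. It would be going too far to infer that the attack rate or the choice of dose is compromised: neither uses these analyses.

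**What to change.** - **Table 27:** state whether Days -2 and -1 count as pre-infection. Compare windows of the same fixed length in each phase. Mean daily severity is an acceptable second choice if its residual inflation (about 2% to 12%) is noted.
- **Lasso window:** take every symptom maximum over Days 2 to 8 for all participants. This keeps the protocol's principle of one window for everyone. It is also safer than the whole challenge period, which ends at discharge and so waits for negative swabs.
- **Performance:** report a bootstrap optimism-corrected or nested cross-validated AUC and cut-point, with selection repeated in every resample.
- **Table 46:** drop the p-values and confidence intervals, or replace them with selection-adjusted ones, and delete the claim that the estimates are unbiased.
- **SAP section 14:** record any remaining departure from Protocol 9.5.4.4.

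The cost is SAP wording, slightly more programming on data already collected, and a lower reported AUC.

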7.1.3. Viral Shedding – Timing, Duration, and Magnitude

Viral shedding is measured by qualitative and quantitative RT-PCR, which are both incorporated into determining viral shedding status (binary yes/no) for a given day, as described in [Section 3.2.2](#).

Qualitative RT-PCR status will be cross-tabulated with RT-qPCR status (RT-PCR+/undetectable) by challenge dose group in [Table 28](#). Qualitative RT-PCR results will be summarized for all targets of the multiplex assays for each study day during the challenge period in [Table 29](#) through [Table 32](#). An overall comparison of qualitative and quantitative RT-PCR results will be presented in [Table 33](#), to assess the agreement of the two assays.

The number of days to first detected viral shedding will be summarized by challenge dose group in [Table 34](#). The median number of days to infection and corresponding 95% CI will be estimated for each group via the Kaplan-Meier method, in order to account for the censoring of participants who never tested RT-PCR+ throughout the challenge period.

The number of total days with RT-PCR+ results will be summarized by challenge dose group in [Table 35](#). A summary of peak viral shedding, total viral shedding (via AUC), and the duration of viral shedding (from first positive through last positive) will be presented in [Table 36](#).

7.2. Exploratory Clinical Analyses

7.2.1. Comparisons of MJS to FLU-PRO

Total FLU-PRO scores will be presented by study day and challenge group in [Figure 11](#), with RT-PCR+ study days annotated on the heatmap, for comparison to [Figure 10](#) for MJS scores.

FLU-PRO symptoms will be summarized by study day for currently infected participants (similarly to MJS symptoms in [Table 19](#) through [Table 22](#)) in [Table 37](#) through [Table 40](#), for a qualitative comparison between the two symptom scoring tools. The maximum severities of symptoms reported during the challenge period will be cross-tabulated between MJS and FLU-PRO in [Table 41](#) (infected participants) and [Table 42](#) (uninfected participants). Cumulative FLU-PRO scores will be summarized by challenge dose group and infection status in [Table 43](#), with maximum cumulative MJS scores (already analyzed as part of the primary endpoint in [Table 14](#)) included for reference.

Scatterplots of each symptom score by total viral shedding (log-10 AUC) will be presented in [Figure 12](#), along with Spearman rank correlation coefficient estimates between each score and the area under the viral shedding curve. Mean total MJS and FLU-PRO scores will be presented by challenge dose group, viral shedding status, and study day during the challenge period, in [Figure 13](#); the entire distributions of symptom scores will be presented in boxplots in [Figure 14](#).

FLU-PRO symptoms will be detailed in [Listing 9](#), and answers to additional FLU-PRO questions will be presented in [Listing 10](#).

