3.2.4. Peak and Total Viral Shedding

Viral copies/mL will be estimated as a mean across quantitative RT-PCR replicates. Some replicates may be dropped from the calculations if potential quality control issues are noted. Values below the lower limit of detection will first be imputed as LOD/2 prior to taking the mean of the replicates.

Peak viral shedding will be calculated as the maximum viral concentration (RNA copies/mL) recorded the duration of the inpatient study period for each individual.

Total viral shedding over the inpatient period will be summarized by the area under the curve (AUC), approximated via the linear trapezoidal method, where the trajectory of an individual's viral concentration is

partitioned into $n-1$ subareas until the last inpatient observation at time t_n . As the linear trapezoidal AUC method approximates the entire area by calculating the cumulative sum of the subareas, the formula that will be applied is:

$$AUC_i = \frac{1}{2} * \sum_{j=1}^{n-1} (t_{j+1} - t_j) * (C_{ij+1} + C_{ij})$$

where $(t_{j+1} - t_j)$ is the difference between the j th and $j+1$ th time points within the inpatient period, and C_{ij} and C_{ij+1} are the viral concentrations measured at the j th and $j+1$ th time points for the i th individual. Intermittent missing values are expected to be minimal, so no imputation is planned.

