5.3.1. Safety (SA) Population

The Safety population will include all participants who received study influenza challenge or sham inoculum.

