14.2 Clinical and Immunogenicity Response Figures

14.2.1 Clinical Response Figures

Figure 7: Maximum Severity of Influenza Symptoms During the Challenge Period by Challenge Dose Group, and Symptom – Infected Participants in the Safety Population

[Implementation Note: The figure shell below is a generic representation that will be updated for solicited influenza symptoms. This figure and the next one correspond to [Table 16](#). All symptoms from MJS, plus fever and lymphopenia, should be included for each panel; Any Symptom will be presented on top. Four panels will include the infected participants from each of the 4 challenge dose groups. Y-axis label will be “Influenza Symptom” and x-axis label will be “Percentage of Participants”.]

[figure not shown]
Similar Figures:

Figure 8: Maximum Severity of Influenza Symptoms During the Challenge Period by Challenge Dose Group, and Symptom – Uninfected Participants in the Safety Population

Figure 9: Maximum Severity of New-Onset Influenza Symptoms During the Challenge Period by Challenge Dose Group, and Symptom – Infected Participants in the Safety Population

Figure 10: Modified Jackson Scores by Study Day, Challenge Dose Group, and Viral Shedding Status – Safety Population

[Implementation note: Total MJS symptom scores will be presented on a by-day basis, sorted by and labeled with challenge dose group on the y-axis (instead of clustering) and with RT-PCR+ study days indicated by an overlaid “+”.]

Similar Figure:

Figure 11: Total FLU-PRO Scores by Study Day, Challenge Dose Group, and Viral Shedding Status – Safety Population

Figure 12: Scatterplots of Maximum Cumulative Modified Jackson and FLU-PRO Scores by Total Viral Shedding – Safety Population

[Implementation note: This is an example figure, for illustration purposes. Only one y-axis and x-axis label will be included, and Spearman rank-order correlation will be estimated between each cumulative score and the log-10-transformed AUC and presented within the relevant figure panel.]

[figure not shown]

Figure 13: Mean Total Modified Jackson and FLU-PRO Scores by Study Day, Viral Shedding Status, and Challenge Dose Group – Safety Population

[Implementation note: This is an example figure, for illustration purposes. Mean total symptom scores will be computed for each study day and each viral shedding subgroup for the given day. A legend to define the groups will also be included.]

[figure not shown]

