Figure 14: Maximum Cumulative Modified Jackson and FLU-PRO Scores by Infection Status and Challenge Dose Group – Safety Population

[Implementation note: This is an example figure, for illustration purposes. A legend to define the groups will also be included, and MJS will be presented on left with FLU-PRO on right.]

[figure not shown]
[figure not shown]

[figure not shown]
Figure 15: ROC Curve from Final Logistic Regression Predicting Influenza Infection Status with the Maximum Severity of Solicited Modified Jackson Score Symptoms, in the Training Data – Safety Population

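### Figure 12's pooled Spearman coefficients mix infected-versus-uninfected separation with any viral load-symptom gradient, so an infected-only coefficient should be added

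*SAP*

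**What the plan says.** SAP 7.2.1 (Comparisons of MJS to FLU-PRO) plans scatterplots of each symptom score against log-10 viral AUC, "along with Spearman rank correlation coefficient estimates between each score and the area under the viral shedding curve". The shell in SAP Appendix 2 is titled "Figure 12: Scatterplots of Maximum Cumulative Modified Jackson and FLU-PRO Scores by Total Viral Shedding – Safety Population". Its implementation note reads: "Spearman rank-order correlation will be estimated between each cumulative score and the log-10-transformed AUC and presented within the relevant figure panel". Neither place restricts or splits the coefficient by infection status or dose.

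Three definitions settle who is in that pool and where they sit:

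- SAP 5.3.1: "The Safety population will include all participants who received study influenza challenge or sham inoculum".
- SAP 3.2.4, on viral load: "Values below the lower limit of detection will first be imputed as LOD/2 prior to taking the mean of the replicates". Participants who never shed therefore sit at or near a common AUC floor.
- SAP 3.2.3 counts a participant as infected if "viral shedding is detected in NP swab(s) by qualitative and/or quantitative RT-PCR on at least two days beginning 24 hours after challenge".

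SAP 5.3 allows analyses in subsets such as infected participants, but does not assign one to Figure 12. Neighbouring displays are split: Tables 41 to 43 by infection status, Figure 13 by shedding status, and "Figure 14: Maximum Cumulative Modified Jackson and FLU-PRO Scores by Infection Status and Challenge Dose Group – Safety Population". None of them gives a load-symptom correlation within the infected.

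**The concern.** With a block of participants at the AUC floor and the infected above it, ranking on AUC is largely ranking on infected versus uninfected. If the infected score higher, which is the premise of the case definition, the coefficient will be positive whether or not heavier shedding goes with worse symptoms. Table 43 and Figure 14 already show that separation.

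Two readings are at stake. The coefficient may be taken as a load-symptom relationship, although its size depends on how many of the enrolled participants were infected. And because the section compares the two tools, the two coefficients will be set against each other. A tool that separates infected from uninfected well can then look as if it tracks viral load well.

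**Working it through.** **The plan's own figures.** The SAP states no correlation to reproduce. The pool size does reproduce. The maximum is 3×12 + 3×12 + 2×17 = 106 active, plus 8 sham = 114. The minimum, through cohorts 1A, 2A, 3A and 3B, is 13 + 13 + 18 + 18 = 62. Both match SAP 4.1.

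**Inputs not in the documents.** The infected share at each dose, the symptom separation and the within-infected correlation are all assumed, and each is varied.

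**Closed form for no relation among the infected.** Let p be the infected share of the pool, q = 1 − p, and A the probability that a random infected participant outscores a random uninfected one. Put all the uninfected at the AUC floor and ignore ties in the scores. On ranks scaled 0 to 1, infected and uninfected differ on average by 1/2 in AUC and by A − 1/2 in score. The covariance is pq × ½ × (A − ½). The rank variances are (1 − q³)/12 for AUC and 1/12 for the score. Hence

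r = 6pq(A − ½) / √(1 − q³).

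Let s and b be the probabilities of a score of 6 or more in infected and uninfected participants, on a normal scale with equal SDs. Then A = Φ[(Φ⁻¹(s) − Φ⁻¹(b))/√2]. This gives 0.771 for s = 0.7, b = 0.3; 0.883 for 0.8, 0.2; and 0.965 for 0.9, 0.1.

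Minimum path (12/12/34 active + 4 sham), infected 30/50/80% by dose: p = (3.6 + 6 + 27.2)/62 = 36.8/62 = 0.594. With A = 0.883, r = 6 × 0.594 × 0.406 × 0.383 / √(1 − 0.067) = 0.57.

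**Simulation** (1,000 runs per setting, integer scores floored at 0). The three values in each cell are for s, b = 0.7, 0.3; 0.8, 0.2; 0.9, 0.1.

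| Setting | p | Closed form, true 0 | Simulated, true 0 | Simulated, true −0.3 | Simulated, true −0.5 |
|---|---|---|---|---|---|
| Minimum, N = 62, infected 30/50/80% | 36.8/62 = 0.594 | 0.41, 0.57, 0.70 | 0.40, 0.57, 0.69 | 0.30, 0.48, 0.62 | 0.24, 0.43, 0.57 |
| Maximum, N = 114, infected 30/50/80% | 56/114 = 0.491 | 0.44, 0.62, 0.75 | 0.43, 0.61, 0.76 | 0.36, 0.56, 0.71 | 0.32, 0.51, 0.68 |
| N = 62, infected 70/85/95% | 50.9/62 = 0.821 | 0.24, 0.34, 0.41 | 0.23, 0.33, 0.41 | 0.05, 0.15, 0.23 | −0.08, 0.04, 0.12 |

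In the first two rows the pooled coefficient was above zero in at least 97% of runs in every setting. Restricted to the infected, the mean estimate was about 0.00, −0.29 and −0.49 for true values of 0, −0.3 and −0.5.

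**Skewed scores and imperfect separation.** A second model used lognormal scores, with infected medians 2 to 4 times the uninfected and infection of 20% to 80% by dose. It placed 10% of the infected at the AUC floor (positive only on the qualitative assay) and 15% of the uninfected above it (positive on one day). For a true within-infected correlation of zero, the pooled mean was about 0.27 to 0.58. With 70/85/95% infected and an inverse relation, it was about −0.01 to 0.22.

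**Comparing the tools.** Suppose one tool is unrelated to load among the infected but has a fourfold infected-to-uninfected median ratio. Suppose the other has a within-infected Spearman of about 0.28 and a twofold ratio. At 20% to 80% infected by dose, the pooled coefficients averaged 0.48 to 0.58 and 0.37 to 0.41. The unrelated tool ranked first in 71% to 98% of runs. With a threefold ratio instead of fourfold, it ranked first in 51% to 86%.

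**When the effect disappears.** If infected and uninfected participants have the same score distribution, the pooled value is about 0 for a true zero and negative (−0.05 to −0.28) for an inverse relation.

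**The case against.** The strongest reply is that the SAP never says the coefficient measures a gradient among the infected. Exploratory objective 6 asks which symptoms best classify infection, and for that aim the uninfected and sham participants are informative. This stands: the pooled coefficient is a valid estimate of the overall association, and it is wrong only for a question the plan does not name. It does not remove the case for an infected-only value, because the quantity plotted is viral load, not infection status, and no other planned display answers the load question.

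The separation is also less clean than the closed form assumes. Infection can rest on the qualitative assay alone while AUC uses quantitative copies, and uninfected includes people positive on one day. The second model allows for both, and the result persists.

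A floor cluster may be visible on the plot, and the shell is not shown, so its markers cannot be checked. The printed coefficient would still be pooled.

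A reader might infer that Figure 12 will always show a clear positive correlation, even against an inverse relation. The documents do not support that. Protocol 4.1 keeps enrolment at the lowest dose only if the attack rate there is at least 80%, so a pool with very high infection is possible, although Protocol 9.3.1 does not expect the first dose to be highly infective. At 70/85/95% infected the pooled value can fall to about zero or below.

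**Conclusion.** The point holds as a minor one. Figure 12 prints one coefficient per tool in which infected-versus-uninfected separation and any load-symptom gradient cannot be told apart. Under assumed infection of 20% to 80% by dose and infected medians 2 to 4 times the uninfected, the coefficient averages about 0.3 to 0.6 with no gradient among the infected. It can be positive when the gradient is inverse. The effect shrinks towards zero as infection becomes near-universal, and it vanishes if infected and uninfected participants score alike.

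It would go too far to read this as an error in the primary analysis. The display is exploratory and descriptive, carries no test or decision, and feeds neither the attack rate nor the choice of dose.

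**What to change.** In Figure 12 and SAP 7.2.1:

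- Add, for each score, the Spearman coefficient among infected participants as defined in SAP 3.2.3, print its n, and name it as the load-symptom measure.
- Keep the pooled coefficient only if it is labelled as mainly reflecting infected-versus-uninfected separation.
- Keep all participants on the scatterplot, with uninfected and sham points marked.

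The cost is one subsetting statement, a label and a plotting symbol. The infected-only coefficient rests on fewer people (30% of 62 is about 19) and still pools doses.

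A separate, optional sensitivity check would put AUC and both scores on Days 2 to 8. The footnotes to Tables 36 and 43 run AUC to discharge and cumulative FLU-PRO over the whole challenge period, while maximum cumulative MJS uses five-day windows within Days 2 to 8. Longer stays could therefore raise FLU-PRO and AUC together. That effect was not simulated, and the main change does not depend on it.
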